Between 20-25 weeks and 30-35 weeks, and at delivery for all women, 20 ml of blood will be drawn (10 for serum, 10 for plasma and isolation of DNA). Cord blood will also be obtained. Both HCQ levels and IFN-α activity will be evaluated in each sample to serve both as a proxy for compliance and as a potential biomarker of efficacy, respectively. Samples will be sent overnight to [name] lab at each visit (screening, 2nd trimester, 3rd trimester, and delivery), rather than having each site process the bloods, which may be unduly cumbersome for busy obstetrical practices. For patients enrolled in Europe, samples will be stored in [name] lab and shipped in batch. Serum samples will be divided into aliquots of 500 □I: 2 will have sodium azide added (final concentration 0.1%) and be stored at 4oC; remaining samples will be stored without azide at -70oC to form the serum specimen bank available to other investigators with approved research protocols (as in the RRNL). Plasma will be similarly stored. DNA will be stored for future investigations as spawned by the clinical results.

Enrolled patients will continue usual care dictated by their underlying rheumatic disease.

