Outcome Measures: The primary outcome is recurrence of advanced heart block: i.e., echocardiogram reveals 2nd or 3rd degree AV block. First-degree block [PR >150 msec, i.e., >(normal mean +3 SD)] [33,39] does not constitute a primary outcome unless it progresses to more advanced block. In these situations the mother will be fully counseled regarding morbidity and mortality of 2nd and 3rd degree block, and discussion regarding data on dexamethasone will be provided. Follow-up will be continued by the patient's treating physician. Secondary outcomes include: 1) Prolonged mechanical PR interval (>150 msec) is detected but does not progress to more advanced AV block. EKG at birth must confirm 1st degree AV block. It is also possible that a fetus developing 1st degree block on study medication might have developed more advanced block in the absence of study medication. The detection of 1st degree block will prompt discussion with the steering committee, treating physician and patient which may lead to treatment with dexamethasone. The mother will be informed of the PRIDE results in which 2 women elected to take dexamethasone and the block reverted to normal sinus rhythm [33]. However, the patient will be informed that we do not know the natural progression or regression of 1st degree block, and that 1st degree block may spontaneously reverse. The mother will continue in the study. 2) Any sign of myocardial injury, without change in cardiac rate or rhythm: a) shortening fraction <28% = 2 SD below normal mean or qualitatively reduced systolic function; b) cardio-thoracic ratio >0.33; c) hydropic changes; d) moderate/severe tricuspid regurgitation. 3) Echocardiographic densities consistent with EFE confirmed postnatally. 4) Fetal death not related to cardiac dysfunction. An autopsy with full evaluation of the heart will be encouraged but cannot be mandated. If AV block or evidence of a cardiomyopathy can be "proven," then these will provide the basis for final categorization. If not possible, the death will not be considered a recurrence rate but will be reported. 5) NL rash. 6) Prematurity (gestational age <37 weeks at birth. 7) Birth weight <10% in the context of gestational age. 8) Abnormal fluid collection.

Evaluation of Ab Levels: This will be done exactly as described for the IVIG trial, using recombinant proteins Ro60, Ro52, and La48 in an ELISA [2].

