Characteristics of the Research Population

Number of Subjects and Subject Recruitment

Stage 1, 19 subjects will be given HCQ. If fewer than 3 recurrences are observed, an additional 51 subjects will be treated in Stage 2 (Years 2-3, seeking a renewal and/or NIH funding). However, if 3 or more recurrences are observed after Stage 1, it will be concluded that HCQ is not effective in preventing CHB. Ultimately, HCQ will be considered efficacious for CHB if fewer than 6 CHB cases occur among 70 subjects evaluated on no potentially confounding medications.

While some subjects will be prescribed the study drug (HCQ) by the PI, [name], or a designated study team member (covered by Consent Form Version 1), many patients will be referred to the study from other sites. In these cases, patients' own doctors will take responsibility for prescribing the study drug, and patients will consent to have their bloods and medical records sent to the investigators at NYU for data and sample analysis (as delineated in Consent Form Version 2). [name] or another study team member will discuss the study with each potential subject and complete the informed consent process prior to enrollment. All subjects (74 in total) will be considered enrolled at NYU and consented using NYU IRB-approved consent forms.

Gender of Subjects

Because the aim of this study is to determine whether hydroxychloroquine use during pregnancy prevents congenital heart block, only female subjects will be recruited.

Age of Subjects

18-45

Racial and Ethnic Origin

No subject will be excluded from participation in this study on the basis of race or ethnic origin.

Eligibility (Inclusion) Criteria

1) Mothers must have anti-Ro and/or anti-La Ab documented in the NYU immunology laboratory (CLIA-approved), which utilizes an ELISA (Immunovision) as well as reactivity on ELISA to at least one of three recombinant antigens (48La, 52Ro, 60Ro, JB laboratory). [name] will likewise

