The proposed design has the following operating characteristics. Let p1 = recurrence rate definitely not worthy of further investigation; p2 = recurrence definitely worthy of further investigation. In this study, we define p1 = 18% [41] and p2 = 5%. According to Simon's optimal 2stage approach [32], the expected sample size is 29.8 subjects with a probability of early termination of 0.69 when the recurrence rate is equal to p1. The probability of accepting the treatment for further study is at most 5% if the recurrence rate is unacceptably high (>18%) with that treatment. In contrast, there is a 90% probability of accepting the treatment for further study if the true recurrence rate is 5%. It is important to emphasize that the purpose is to obtain critical data on the efficacy of HCQ in the prevention of recurrent CHB and determine whether this preventive approach should be studied further. At study completion, the proportion of mothers having a child with advanced CHB will also be computed, along with corresponding 95% confidence intervals. Secondary endpoints that are binary (i.e., occurrence of 1st degree block, abnormal fluid collection) will be analyzed by similar approaches. Continuous variables (e.g., shortening fraction, gestational age) will be summarized by estimating means and standard deviations. The effect of therapy on HCQ levels, IFN-α signatures, and Ab titers will be evaluated by fitting mixed effects linear models to repeated assessments of titers obtained during follow-up. In addition, change in any of these analytes at specific time points from baseline will be analyzed using the paired t-test or Wilcoxon signed rank test, depending on distribution of the data.

Safety committee. An independent DSMB will convene by teleconference three times during the year. The members include Drs. [name], [name], and [name] (all of whom served in PITCH).

Data Storage and Confidentiality

Data management. Study information will be recorded at the patients' obstetrical and rheumatology sites. Standardized, computer-adapted case report forms (CRFs) have been developed. Within 2 weeks of each visit, completed CRFs and tapes of the echocardiograms will be sent to [name]. Following review, CRFs will be faxed to the coordinator at NYU for final error checks and entered into the computer database. The coordinator will maintain a calendar for each patient, monitor completion

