Safety committee. An independent DSMB will convene by teleconference three times during the year. The members include Drs. [name], [name], and [name] (all of whom served in PITCH).

Individual stopping rules: Fetal: 1) Development of advanced block (2nd or 3rd degree); 1st degree block will not constitute a formal stopping point. 2) Decrease of amniotic fluid index <5 cm. 3) Intrauterine growth restriction (IUGR) - no fetal growth over 2 weeks. 4) Hydrops or myocardial dysfunction or EFE. 5) Death. Maternal: 1) Serious reaction to study drug, e.g. severe rash or intractable G.I. intolerance. 2) Withdrawal of consent. If isolated 1st degree heart block occurs, dexamethasone may be offered, and the patient may continue in the study. If a patient achieves an individual stopping point due to CHB and hydropic changes, she will be offered dexamethasone and the outcome of the pregnancy will be prospectively followed.

Study stopping rules: Enrollment is stopped if 3 fetuses develop 2nd or 3rd degree block.

Potential Benefits to the Subjects

We hope that this study shows that treatment with hydroxychloroquine prevents the development of heart block in your baby.

The potential benefits are substantial in relation to the small risks posed by participation.

This study is important because there is information from basic science research suggesting that hydroxychloroquine may be effective in preventing the inflammation and fibrosis which may result in heart block. This is only testing done with test tubes, not animals or humans. There is also a large study that reviewed the charts of many women with anti-Ro antibodies and this study found that hydroxychloroquine may be beneficial. However, we also are not sure whether for those mothers who received hydroxychloroquine, they may have had normal babies even without taking the drug. The results of this study will be used not only for a potential benefit to your own baby but also as a guide to help other pregnancies in which the baby is at risk for heart disease.

Subject Identification, Recruitment and Consent/Assent

Method of Subject Identification and Recruitment

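### The final efficacy count is limited to women free of undefined confounding drugs, so a recurrence after dexamethasone for first-degree block may fall outside it

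*Combined protocol and SAP*

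**What the plan says.** All references are to the combined protocol and SAP.

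- **Final decision** (Number of Subjects and Subject Recruitment): HCQ is efficacious if "fewer than 6 CHB cases occur among 70 subjects evaluated on no potentially confounding medications". The same section says "All subjects (74 in total) will be considered enrolled at NYU" and does not explain the four women above 70.
- **Primary outcome** (Outcome Measures): first-degree block "does not constitute a primary outcome unless it progresses to more advanced block". No exception is made for women given dexamethasone.
- **Rescue treatment**: under Outcome Measures, detection of first-degree block starts a discussion "which may lead to treatment with dexamethasone", and the mother remains on study. Individual stopping rules (Protection Against Risks) agree: "dexamethasone may be offered, and the patient may continue in the study".
- **Other drugs**: at the end of the follow-up and sampling text in Study Design, "Enrolled patients will continue usual care dictated by their underlying rheumatic disease". Prednisone up to 20 mg/day is allowed at entry, and more is an exclusion.
- **Counts without a medication restriction**: the Stage 1 rule (3 or more of 19), the study stopping rule (3 fetuses with second- or third-degree block), and the final estimate, where "the proportion of mothers having a child with advanced CHB will also be computed" with a 95% confidence interval (Data Analysis And Data Monitoring).

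The medication clause appears once. No section of the supplied text lists the drugs, gives a dose or timing, or says whether an exposed woman is excluded, replaced or analysed separately.

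**The concern.** The outcome definition says what counts as an event. The medication clause says which women are in the decision. The plan does not reconcile the two.

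If dexamethasone is one of the confounding drugs, a fetus that shows first-degree block, is treated, and still progresses to advanced block is a primary outcome event whose mother may be outside the 70. The decision set would then be selected on a post-enrolment treatment that is itself triggered by a possible early sign of the endpoint. If usual-care rheumatic drugs were meant instead, there is no such link to fetal disease, but who counts is still open.

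On either reading, the yes/no decision and the reported recurrence rate can rest on different women. The trial is open-label, so without a written list the set could be fixed once outcomes are known.

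**Working it through.** **Inputs.** Stage 1 has 19 women and continues with at most 2 recurrences. Stage 2 adds 51. Efficacy needs at most 5 of 70. The unacceptable rate is 18% and the target rate 5%. I also show 10%, an intermediate rate that the plan uses in its randomised-trial power calculation. The three-case stop is taken as the Stage 1 rule.

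**Formula.** With Stage 2 (or the open part of it) of size n2 and final limit c, the chance of declaring efficacy at true rate p is

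A(p, n2, c) = Σ over k = 0, 1, 2 of b(k; 19, p) × B(c − k; n2, p),

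where b is the binomial probability and B the cumulative binomial.

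**The plan's own figures.** At 18% the chance of stopping after Stage 1 is 0.691, matching the stated 0.69. The stated expected size of 29.8 and power of 90% do not reproduce with 70 women: expected size is 19 + 51 × 0.309 = 34.8, and power at 5% is 0.831. They do reproduce with 54 women (29.8 and 0.903; type I error 0.049). That is a separate matter. The baseline below is the rule as written, with 70.

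**Baseline at 10%.** A(0.10, 51, 5) = 0.1351 × 0.5976 + 0.2852 × 0.4131 + 0.2852 × 0.2364 = 0.0807 + 0.1178 + 0.0674 = 0.266.

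**One woman dropped.** Replacement is an assumption, compatible with 74 enrolled against 70 counted.

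| Case | Expression | 5% | 10% | 18% |
|---|---|---|---|---|
| Nobody dropped | A(p, 51, 5) | 83.2% | 26.6% | 0.75% |
| One recurrence dropped and replaced | A(p, 52, 6) | 89.0% | 37.8% | 1.65% |
| One treated Stage 2 woman progressed, counted | A(p, 50, 4) | 72.2% | 16.2% | 0.29% |
| One treated Stage 2 woman did not progress, counted | A(p, 50, 5) | 83.7% | 27.8% | 0.86% |
| Either of those women dropped and replaced | A(p, 51, 5) | 83.2% | 26.6% | 0.75% |

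At 10%, dropping a treated progressor moves acceptance from 16.2% to 26.6%, which favours HCQ. Dropping a treated non-progressor moves it from 27.8% to 26.6%, which goes against HCQ.

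**Direction.** Let q be the chance that a treated woman's fetus progresses. The two effects cancel when q = [A(p,50,5) − A(p,51,5)] / [A(p,50,5) − A(p,50,4)]. This gives 0.05, 0.10 and 0.18 at the three rates, so break-even is q = p. The documents do not fix q. In PRIDE, "2 women elected to take dexamethasone and the block reverted to normal sinus rhythm" (Outcome Measures): 0 of 2 progressed, with a 95% upper limit of 1 − 0.025^(1/2) = 84%. The Background (Prenatal Considerations) describes dexamethasone's effect on incomplete block as inconsistent.

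**Range over plausible numbers.** Assume a share d = 1/74 or 2/74 takes dexamethasone and q lies between 0 and 0.5. Untreated women then have rate (p − dq)/(1 − d). Stage 1 counts all 19 women, and the final rule uses 70 untreated women. For d = 2/74 and p = 10%, the untreated rate is 0.100/0.973 = 10.3% at q = 0 and (0.100 − 0.0135)/0.973 = 8.9% at q = 0.5. Acceptance over this range runs from 24.4% to 35.3% at 10% (baseline 26.6%), and from 0.58% to 1.1% at 18% (baseline 0.75%).

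**One woman and the threshold.** Suppose 6 of the first 70 women have a recurrence: the rule fails. Drop one who had dexamethasone, add a 71st woman without recurrence, and the count is 5/70 (7.1%): the rule passes. All 71 women give 6/71 (8.5%).

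**The case against.** The best defence is that little is really open. Outcome Measures already makes progression a primary outcome with no dexamethasone exception, the stopping rule counts it, and the final proportion reports it. No section calls dexamethasone confounding. Prednisone, the one usual-care drug for which the plan sets a limit, is handled at entry. Testing HCQ without rescue steroid is a fair aim for a Phase II screen, and counting treated non-progressors as HCQ successes is the confounding that the clause seems meant to avoid. The largest movement is at 10%, which is neither design rate. None of the three recurrences in the US IVIG study (PITCH) followed a prolonged PR interval, so few women may be affected.

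Most of this stands, and it limits the size of the point. It does not close the gap: defining the event does not settle who is in the 70, and an HCQ-alone decision would also need a drug list, a time window and a replacement rule.

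A further objection concerns the remedy. Women enter by 12 weeks and the first fetal echocardiogram is at 16-18 weeks. Counting the first 70 enrolled without replacement would make early losses into non-recurrences. With four unevaluable Stage 2 women (an assumption), A(p, 47, 5) is 31.4% at 10% and 1.24% at 18%, a shift of similar size to the problem. This is right, and the remedy must use evaluable women.

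A reader might infer that the clause inflates the false-positive rate beyond 5%, or that it plainly favours HCQ. The documents support neither. The type I error is 1.65% with one recurrence dropped and replaced. Leaving two recurrences out of the final count of 70 (limit of 7) gives 3.8%. The sign of the bias depends on q, which is unknown.

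**Conclusion.** The point holds in a limited form. The final decision rests on an undefined set that may exclude women given dexamethasone for on-study first-degree block, including any whose fetus then progresses to a primary outcome. The other three counts in the plan carry no such restriction.

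The size is modest: with one or two treated women and q up to 50%, acceptance moves by no more than about 9 percentage points at 10% (26.6% to 35.3%) and stays near 1% at 18%. The direction is not determined. These figures assume that dexamethasone is among the confounding drugs, that dropped women are replaced, and the stated values of d and q.

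It would also be wrong to infer that recurrences would go unreported, since the final proportion has no medication restriction. What is at risk is the yes/no decision, which one woman can turn and which could be settled after the data are seen. This should be corrected, but it does not invalidate the design.

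**What to change.** - **Decision set.** Apply the limit of fewer than 6 to the first 70 evaluable women: eligible, treated with HCQ, and with fetal echocardiographic outcome data. Count every second- or third-degree block, whatever medication was started after enrolment. Replace only women who are unevaluable for reasons unrelated to medication or fetal conduction findings.
- **Secondary analysis.** Report the HCQ-alone set, with the confounding drugs (dexamethasone and any usual-care drugs) listed in advance.
- **Sensitivity analysis.** Count each dexamethasone start before advanced block as a recurrence. Label this a worst-case bound that leaves the primary endpoint unchanged. It is needed because dexamethasone might itself prevent progression.

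**Cost.** A few sentences. Women with first-degree block already stay in the study, so no echocardiograms are added for them. The downside is that the primary result reflects HCQ plus any rescue dexamethasone, which the sensitivity analysis bounds.

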Accordingly, a multicenter, prospective, open-label study in the U.S. was initiated [2] (Preventative IVIG Therapy for CHB, PITCH). Enrollment criteria included the presence of anti-Ro Ab in the mother, birth of a previous child with CHB/neonatal lupus rash, current treatment with 20 mg/day of prednisone, and <12 weeks pregnant. IVIG (400 mg/kg) was given every 3 weeks from gestational week 12 - 24. The primary outcome was the development of 2nd or 3rd degree CHB. Twenty mothers completed the IVIG protocol before the predetermined stopping rule of 3 cases of advanced CHB was reached. CHB was detected at 19, 20, and 25 weeks; none occurred following a prolonged PR interval. One of these 3 mothers had 2 previous children with CHB. One child without CHB developed a transient rash consistent

with neonatal lupus. Sixteen children had no manifestations of neonatal lupus at birth. No significant changes in maternal titers of Ab to Ro60, Ro52, or La48 were detected over the course of therapy or at delivery. There were no safety issues.

In parallel with enrollment of the PITCH study, a European study was initiated in December, 2004. We and the P.I., [name], had agreed on the protocol. The study was terminated after 3 recurrent cases of CHB were identified following enrollment of 15 mothers [3]. Combining data generated from the U.S. and the European PITCH studies, there were 6 (18%) recurrences in 33 women who had previous pregnancies complicated by CHB. Each study was originally designed to conclude inefficacy of IVIG if 6 cases of 54 were identified. However, since the chances of one further recurrence in the next 21 (if combined US and UK) was greater than 98% assuming the 18% recurrence rate observed, the trial was deemed futile and terminated.

Hydroxychloroquine: A potential prophylactic approach

Antimalarials are among the most frequently prescribed medications in SLE patients. The prevention of flares and reduction of mortality are associated with the use of these medications as supported by a recent systematic review of high quality published evidence [20]. Serious adverse events such as cardiotoxicity are rare, even after prolonged use. With regard to retinal toxicity, CQ appears to be more toxic than HCQ [20].

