Another potential mechanism favoring efficacy in preventing CHB, is that HCQ by virtue of reducing endosomal acidification might also decrease transplacental transport of maternal antibodies. This possibility is supported by the fact that maternal IgG is pinocytosed at the apical surface of the syncytiotrophoblast into an acid endosomal compartment containing FcRn, and migrates via transport vesicles to the basolateral surface of the cell, where at physiologic pH it uncouples from the receptor (15).

Study Design

Nineteen women in Stage 1 and an additional 51 women in Stage 2 (if reached, for a total of 70 subjects) meeting eligibility criteria will receive 400mg per day of HCQ beginning as soon as pregnancy is established and informed consent obtained. Mothers already on HCQ will remain on 400mg, or escalate to 400mg if on 200mg. The primary investigator, [name]., holds a U.S. Federal Drug Administration-issued IND (Investigational New Drug) number (112357) for HCQ.

A. Screening visit: Prior to the qualifying visit, the consent form will be reviewed and signed. Laboratory tests will include: CBC, liver-function tests (routine chemistries; albumin will be important to standardize the effect of physiologic hemodilution of pregnancy in gauging changes in autoantibody titers), urinalysis, and a 24 h collection for measurement of creatinine clearance and protein excretion as deemed appropriate. Serologic profiles will include: measurement of ANA, anti-DNA, C3 and C4. Blood will be drawn for baseline anti-Ro/La titer HCQ level, and IFNαactivity. Only the former will be available prior to qualification for enrollment. In total, 35 ml of blood will be drawn at screening.

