With over 400 families now enrolled in the RRNL and our success at rapid enrollment in PITCH, we are well positioned to enroll in the current study. Most of the women enrolled in the RRNL are of childbearing age, motivation is quite high, and based on review of overall data, it is likely that at least 20% will again become pregnant and available for this study. Importantly, PRIDE and PITCH solidified a referral base of obstetricians and pediatric cardiologists. Furthermore, [name] has agreed to participate given that all 19 patients must be recruited in one year. The DSMB for the U.S. based PITCH study ([name], maternal-fetal medicine, [name], rheumatologist with expertise in pregnancy and women's health issues, and [name], rheumatologist with expertise in design and monitoring of clinical trials in SLE) in conjunction with Drs. [name], [name], [name] (pediatric cardiologist), and [name] (statistician) have had extensive discussions regarding the results of PITCH and the design of this current study. With regard to a randomized trial comparing any drug with placebo, [name] prepared the following analysis:

Assumptions 1. Recurrence rate of CHB (whether previous child had CHB or rash) is approx 19%.

2. Clinically meaningful outcome would be at least 50% reduction in recurrence rate.

Power Calculations 19% to 10% recurrence rate: 261 per group (N = 522)

19% to 5% recurrence rate: 97 per group (N = 194)

Data Analysis And Data Monitoring

Statistical considerations for overall study:

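### The printed 90% power and expected sample size of 29.8 do not belong to the written 19/70, fewer-than-6 rule, which has 83% power and an expected sample size of 34.8

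*Combined protocol and SAP*

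**What the plan says.** Under Data Analysis And Data Monitoring (Statistical considerations for overall study), the protocol sets an unacceptable recurrence rate of 18% and a desirable rate of 5%, invokes Simon's optimal two-stage approach, and prints four operating characteristics for the proposed design:

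- at 18%, "the expected sample size is 29.8 subjects";
- a probability of early termination of 0.69 at 18%;
- at most a 5% chance of accepting the drug if the rate is unacceptably high;
- "there is a 90% probability of accepting the treatment for further study if the true recurrence rate is 5"%.

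That section does not print the sample sizes or cut-offs. They are elsewhere:

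- Study Design: "Nineteen women in Stage 1 and an additional 51 women in Stage 2 (if reached, for a total of 70 subjects".
- Number of Subjects and Subject Recruitment, stage 1: "if 3 or more recurrences are observed after Stage 1, it will be concluded that HCQ is not effective in preventing CHB".
- Same section, final decision: "HCQ will be considered efficacious for CHB if fewer than 6 CHB cases occur among 70 subjects evaluated on no potentially confounding medications".
- Same section, enrolment: "All subjects (74 in total) will be considered enrolled at NYU".

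The number 54 appears only in the Background, for the earlier IVIG trials: "Each study was originally designed to conclude inefficacy of IVIG if 6 cases of 54 were identified".

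**The concern.** With the cut-off fixed at fewer than 6 cases, every added woman makes success harder to reach at any given recurrence rate. A rule of 5 or fewer in 70 is much stricter than 5 or fewer in 54, so the two cannot share the same power. Nor can a design with a 51-woman second stage have the expected size printed, once the early-termination probability is 0.69.

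The figures describe the primary go/no-go decision. If power is overstated, a negative result will be read as stronger evidence against hydroxychloroquine than it is. The denominator can also change the verdict. Five cases in the first 54 women and a sixth among the last 16 is a success on a 54-woman reading and a failure on the written 70-woman reading.

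**Working it through.** **Inputs.** Rates of 18% and 5% come from the statistical considerations. Stage sizes n1 = 19 and n2 = 51 come from Study Design. The rules (continue with 0–2 cases of 19, accept with 5 or fewer of 70) come from Number of Subjects and Subject Recruitment.

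**Formulas** (exact binomial, N = 19 + n2, final limit r):

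- PET(p) = P[Bin(19, p) ≥ 3]
- E[N](p) = 19 + n2 × (1 − PET)
- Accept(p) = Σ over x = 0, 1, 2 of P[Bin(19, p) = x] × P[Bin(n2, p) ≤ r − x]

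**Step 1: reproduce the printed figures.** An exhaustive search for Simon's optimal design (18% versus 5%, error at most 0.05, power at least 0.90) returns n1 = 19, continue if 2 or fewer, N = 54, accept if 5 or fewer. For that design n2 = 35:

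- PET at 18% = 0.691.
- E[N] at 18% = 19 + 35 × 0.309 = 29.81.
- Accept at 18% = 0.0230 × 0.3789 + 0.0961 × 0.2196 + 0.1898 × 0.1026 = 0.0493.
- Accept at 5% = 0.3774 × 0.9927 + 0.3774 × 0.9710 + 0.1787 × 0.9042 = 0.903 (unrounded 0.9026).

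All four printed figures are matched. Working backwards from the printed expected size gives the same answer: (29.8 − 19) / 0.309 ≈ 35, so N = 54.

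**Step 2: the written rule, n2 = 51, N = 70, r = 5.**

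- PET at 18% = 0.691, unchanged because it depends only on stage 1.
- E[N] at 18% = 19 + 51 × 0.309 = 34.76.
- Accept at 18% = 0.0230 × 0.0833 + 0.0961 × 0.0352 + 0.1898 × 0.0118 = 0.0075.
- Accept at 5% = 0.3774 × 0.9589 + 0.3774 × 0.8896 + 0.1787 × 0.7494 = 0.8315.

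| | Printed | 5 or fewer of 54 | 5 or fewer of 70 (written) |
|---|---|---|---|
| Power at 5% | 90% | 90.3% | 83.1% |
| E[N] at 18% | 29.8 | 29.8 | 34.8 |
| PET at 18% | 0.69 | 0.691 | 0.691 |
| Error at 18% | at most 5% | 4.93% | 0.75% |

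**Step 3: where the power goes.** At a true 5% rate the drug is rejected with probability 1 − 0.8315 = 16.9%. Stage 1 accounts for 6.7 points under either N. The final cut-off accounts for 10.2 points with 70 women and 3.1 points with 54. Under the written rule, power reaches 90% only if the true rate is about 4.2% or lower.

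**Step 4: other boundaries with the same stage 1.**

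| Accept if | Error at 18% | Accept at 12% | Power at 5% | Exact 95% CI at the boundary |
|---|---|---|---|---|
| 5 or fewer of 70 | 0.75% | 12.9% | 83.1% | 2.4–15.9% |
| 6 or fewer of 70 | 1.85% | 21.7% | 89.3% | 3.2–17.7% |
| 7 or fewer of 70 | 3.8% | 31.5% | 92.0% | 4.1–19.5% |
| 5 or fewer of 54 | 4.93% | 30.8% | 90.3% | 3.1–20.3% |

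The intervals are not adjusted for the two stages.

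**The case against.** **Seventy may be enrolled and 54 evaluable.** That would rescue every printed figure. But the success criterion is applied to 70 women evaluated, a separate total of 74 is given for enrolment, and no passage names a 54-woman set for this trial. The carry-over from a 54-subject design remains an inference.

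**Expected size.** If stage 1 stopped at the third case instead of after 19 women, E[N] at 18% for the 70-woman rule would be 29.9, close to the printed value. The Specific Aim and the recruitment section place the decision after stage 1, and the exact match with 54 is the likelier source. Power is 83.1% either way, so the expected-size discrepancy is secondary.

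**Study stopping rule.** Under Protection Against Risks, enrolment stops at three cases of advanced block, with no limit to stage 1. Applied to all 70 women, acceptance at a 5% rate would be about 31%. The Specific Aim ties this stop to the first stage, and the fewer-than-6 criterion would have no meaning otherwise, so the stage 1 reading is the coherent one. The 83% does rest on it.

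**The rule is conservative.** This is true and has value: the error is 0.75% instead of 4.9%, and the protocol also calls for a 95% confidence interval, which limits over-reading. It does not make the 90% correct. The cost falls on the chance of recognising a drug that meets the plan's own target.

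**Conclusion.** The concern holds. For the rule as written, power at a 5% recurrence rate is 83.1%, not 90%, and expected sample size at 18% is 34.8, not 29.8. The risk of missing a drug at the target rate is 16.9%, about 1.7 times the 10% implied. The early-termination probability and the error limit are correct as printed. The calculation uses only the protocol's own rates, sizes and cut-offs. It assumes independent outcomes, a stage 1 decision after 19 women, and a three-case stop that applies to stage 1 only. Because these are the only operating characteristics given for the primary decision, the text must be corrected.

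**What to change.** **Preferred.** Keep the 19/70, fewer-than-6 rule. In the statistical considerations, print the sample sizes and cut-offs next to the operating characteristics, and restate power as 83% at 5%, expected sample size as 34.8 at 18%, and error as 0.75%. Early termination stays at 0.69. This changes wording only: no extra patients and the same decision rule, with less favourable printed power.

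**If 54 evaluable women is the intended decision set.** Say so, apply fewer than 6 to the first 54 (19 + 35), and state how the other 16 women are used. The printed figures then hold.

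**If 90% power at 70 women is wanted.** Fewer than 8 of 70 gives 92.0%. Fewer than 7 gives 89.3%, just short.

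The last two options relax the written boundary: acceptance at a true 12% rate rises from 12.9% to between 21.7% and 31.5%. They are design changes, to be justified and, in an open-label trial, fixed without knowledge of accumulating outcomes.

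Whichever is chosen, define what 70 (evaluated) and 74 (enrolled) mean and which is the denominator. Also reconcile the three-case enrolment stop under Protection Against Risks with the stage 1 rule, since the restated power depends on how it is read.
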